5.4.3 Intra-Patient Escalation

Intra-patient dose escalation is not allowed.

5.5 **Grading of Adverse Events**

Adverse events (toxicities) will be graded according to the NCI Common Terminology Criteria for Adverse Events (CTCAE) version 5.0. All appropriate treatment areas should have access to a copy of the CTCAE version 5.0. A copy of the CTCAE version 5.0 can be downloaded from the CTEP web site http://ctep.cancer.gov/protocolDevelopment/electronic_applications/ctc.htm. Any suspected or confirmed dose-limiting toxicity should be reported immediately (within 24 hours) to the Study Chair.

5.6 **Definition of Dose-Limiting Toxicity (DLT)**

DLT will be defined as any of the following events. The DLT observation period for the purposes of dose-escalation will be the first cycle of therapy. Refer to [Section 6.3](#) for specific criteria for patients < 12 months of age at the time of the non-hematological DLT.

Dose limiting hematological and non-hematological toxicities are defined differently.

5.6.1 Non-hematological dose-limiting toxicity for patients \geq 12 months of age:

5.6.1.1 All Grade 3 or greater non-hematological toxicity not clearly related to the underlying disease and attributable to protocol therapy will be considered a DLT except:

- Grade 3 nausea and vomiting < 3 days duration
- Grade 3 elevation of ALT/AST/bilirubin, that returns to Grade ≤ 1 or baseline prior to the time for the next treatment cycle.
NOTE: For the purposes of this study the ULN for ALT is defined as 45 U/L and for AST is defined as 50 U/L. Adverse event grades will be based on increases above the upper limit of normal, regardless of the subject's baseline. See [section 5.6.3](#) and [6.2.4](#). See [Appendix III](#) for nomogram.
- Grade 3 hypophosphatemia (See [section 6.2.5](#)), hypokalemia, hypocalcemia or hypomagnesemia responsive to supplementation.
- Grade 3 arthralgia/myalgia that returns to Grade ≤ 1 prior to the start of the next cycle or within 14 days of optimizing oral analgesics (whichever is shorter).

5.6.2 Non-hematological dose-limiting toxicity for patients < 12 months of age:

5.6.2.1 Any \geq Grade 2 non-hematological toxicity not clearly related to the underlying disease and attributable to the protocol therapy will be considered a DLT with the specific exclusion of Grade 2 liver enzyme

elevation, including ALT/AST/bilirubin, that returns to Grade ≤ 1 or baseline prior to the time for the next treatment cycle.

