6.2 Dose Modifications for Non-Hematological Toxicity (for patients \geq 12 months)

6.2.1 Patients who have any dose-limiting non-hematological toxicity (as defined in [Section 5.6.1](#)) may continue on protocol therapy upon meeting eligibility lab requirements or baseline but should receive subsequent doses of pevonédistat at the next lower dose level. Irinotecan and temozolomide should be continued at the same dose.

6.2.2 If the same non-hematological dose-limiting toxicity recurs after one dose reduction, the patient must be removed from protocol therapy.

6.2.3 Patients who have a dose-limiting non-hematological toxicity that does not resolve to baseline or eligibility within 21 days after the planned start of the next treatment cycle must be removed from protocol therapy.

6.2.4 Pevonédistat dose modification for hepatic toxicity:

In all cycles, AST, ALT, and bilirubin should be checked prior to each dose of pevonédistat and then once weekly for the remaining weeks of the study. It is anticipated that LFTs (AST, ALT, and occasionally bilirubin) may be elevated for approximately 48 hours following the end of the 1st pevonédistat infusion. See [Appendix III](#) for toxicity grading table.

For Grade 2 or 3 AST, ALT, or bilirubin on or after Cycle 1 Day 8, pevonédistat should be held. Once the elevated AST, ALT, or bilirubin returns to \leq Grade 1 by the end of the current cycle, then pevonédistat dose may be resumed at the same dose. If a dose is delayed due to increased LFTs, pevonédistat needs to be administered by Day 25 of Cycle 1 or Day 18 of subsequent cycles (within a cycle there should be a maximum of 13 days between doses).

For Grade 4 AST, ALT, or bilirubin on or after Cycle 1 Day 8, the pevonédistat dose should be held for the remainder of the cycle. If the elevated AST, ALT, or bilirubin return to \leq Grade 1, then pevonédistat may be restarted at the next cycle at the next lower dose level.

Interventions for Dose Modifications Secondary to Elevated AST, ALT, or bilirubin	
Grade 2	Hold pevonédistat until resolved to \leq Grade 1
Grade 3	Hold pevonédistat until resolved to \leq Grade 1
Grade 4	Hold pevonédistat for remainder of cycle. For subsequent cycle resume at next lower dose level if resolved to \leq Grade 1

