For pevonédistat, a minimum of 1 full calendar day between any 2 doses should be maintained, and a maximum of 3 doses of pevonédistat within Cycles 2+ must not be exceeded. There should be a maximum of 13 days between doses within a given cycle.	

6.2.5 Pevonedistat dose modification for hypophosphatemia:

If hypophosphatemia is \geq Grade 3, study drug treatment should not be resumed until the hypophosphatemia is \leq Grade 2. Hypophosphatemia should be evaluated (including severity and etiology), monitored, and treated according to institutional guidelines.

6.3 Dose Modifications for Non-Hematological Toxicity (for patients < 12 months at the time of the DLT)

Patients less than 12 months of age who have a \geq Grade 2 non-hematological toxicity attributable to the study drug will have pevonedistat held as per [Section 6.2](#) and this will be considered a DLT with the specific exclusion of Grade 2 liver enzyme elevation, including ALT/AST/bilirubin, that returns to Grade \leq 1 or baseline prior to the time for the next treatment cycle (see [Section 6.2.4](#)). Patients should receive subsequent cycles of the drug but with dose modifications according to [Section 6.2](#).

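### After a recovered Grade 3 liver DLT in a patient under 12 months, Section 6.3 does not say whether 6.2.1 (reduce) or 6.2.4 (same dose allowed) governs, so full-dose re-treatment is permitted

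*Combined protocol and SAP*

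**What the plan says.** **DLT definitions.** For patients under 12 months, Section 5.6.2.1 says that non-hematological toxicity of Grade 2 or more that is "attributable to the protocol therapy will be considered a DLT with the specific exclusion of Grade 2 liver enzyme" elevation that recovers before the next cycle. Section 6.3 repeats this. A recovered Grade 3 elevation is not excluded, so it is a DLT. For patients 12 months or older, Section 5.6.1.1 does exempt it; the exception there reads "Grade 3 elevation of ALT/AST/bilirubin, that returns to Grade" 1 or baseline in time for the next cycle.

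**Dose rules.** Section 6.2 is headed for patients 12 months or older. Its first item, 6.2.1, covers "Patients who have any dose-limiting non-hematological toxicity (as defined in" Section 5.6.1); they "may continue on protocol therapy upon meeting eligibility lab requirements or baseline but should receive subsequent doses of" pevonedistat at the next lower level. Section 6.2.4 deals with the liver. Its rule begins "For Grade 2 or 3 AST, ALT, or bilirubin on or after Cycle 1 Day 8": hold pevonedistat, and once the value is back to Grade 1 or less by the end of the cycle, the "dose may be resumed at the same dose". For Grade 4 the 6.2.4 table says "For subsequent cycle resume at next lower dose level if resolved to" Grade 1 or less.

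**The link for infants.** Section 6.3 has no dose rule of its own: "Patients should receive subsequent cycles of the drug but with dose modifications according to" Section 6.2. It names the whole section and gives no order of precedence within it.

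**The concern.** The infant DLT definition was made stricter, but the dose rules were written around the older-patient definition and brought across unchanged. For one event, a recovered Grade 3 liver elevation, this leaves a site with a direction to reduce and a permission not to. A site relying on 6.2.4 could give an infant the full dose again after a liver DLT, in the same cycle or the next.

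Liver toxicity is the DLT to expect with this drug. Section 2.6 calls hepatotoxicity the predominant adult DLT, and in the adult solid-tumor combination study described in Section 2.3.1, 8 of the 12 patients with DLTs had raised liver tests (8 of 58 enrolled, 13.8%). No infant had been treated on this study by the date given in Section 11.1, so the infant rate is unknown.

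There is also a knock-on effect. Section 6.2.2 removes a patient when the same DLT recurs after one dose reduction. If the dose was never reduced, a second Grade 3 liver DLT at full dose does not meet that condition.

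**Working it through.** The plan gives no figure to reproduce. The check traces each liver event through the rules, assuming the event is attributable to protocol therapy, occurs on or after Cycle 1 Day 8, and (for Grades 2 and 3) recovers to Grade 1 or less within the cycle.

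| Event | DLT? | 6.2.1 | 6.2.4 | Same answer? |
|---|---|---|---|---|
| 12 months or older, Grade 3 | No (5.6.1.1) | not triggered | same dose | yes |
| 12 months or older, Grade 4 | Yes | next lower level | next lower level | yes |
| Under 12 months, Grade 2 | No (5.6.2.1) | not triggered | same dose | yes |
| Under 12 months, Grade 3 | Yes (5.6.2.1, 6.3) | next lower level, if the infant definition is substituted | same dose | **no** |
| Under 12 months, Grade 4 | Yes | next lower level | next lower level | yes |

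The gap is confined to one row. It can be read in two ways.

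1. *Substitute the infant DLT definition in 6.2.1.* Then 6.2.1 directs a reduction and 6.2.4 permits none.
2. *Take the reference in 6.2.1 to Section 5.6.1 literally.* Then 6.2.1 is silent, because 5.6.1.1 exempts the event, and only the same-dose rule remains. On this reading 6.2.1 also misses every DLT that exists only under 5.6.2, such as a Grade 2 non-hepatic DLT in an infant.

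**Elevations covered** (Appendix III, with the study ULN of 45 U/L for ALT and 50 U/L for AST):
- ALT 226 to 900 U/L: 226/45 = 5.02 and 900/45 = 20 times ULN.
- AST 251 to 1000 U/L: 251/50 = 5.02 and 1000/50 = 20 times ULN.
- Bilirubin above 3 and up to 10 times ULN.

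**Dose difference** (levels from Section 5.4.1; three doses per cycle from Cycle 2 on; percentage = (same − reduced)/reduced):
- Level 3: 25 against 20 mg/m² per dose, 5/20 = 25% higher. Per cycle, 3 × 25 = 75 against 3 × 20 = 60, or 15 mg/m² more.
- Level 4: 35 against 25 mg/m² per dose, 10/25 = 40% higher. Per cycle, 105 against 75, or 30 mg/m² more.

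**How many infants.** Section 11.1 (Amendment 5) plans 6 at level 3 and 6 at level 4, so 12 evaluable, and 12/0.8 = 15 enrolled. Section 2.6 reports one patient each with Grade 3 AST and Grade 3 ALT among 18 evaluable older children; the text does not settle whether this is one child or two. If infants had the same rate, which is an assumption, the expected number is 12 × 1/18 = 0.7 to 12 × 2/18 = 1.3.

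**The case against.** The strongest reply is that the text can be made to work. Section 6.2.1 says *should* and 6.2.4 says *may*, so a site that reduces the dose complies with both. In 6.3 the pointer to 6.2.4 closes the clause on the recovering Grade 2 elevation, which is not a DLT. The next sentence then speaks of dose modifications, which fits the reduction in 6.2.1. This is a fair argument and it stands in part. A reader might infer that the plan contains two mandatory rules in flat contradiction; the documents do not support that, and reduction is the better reading.

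It does not close the gap. The final sentence of 6.3 imports all of 6.2, including the same-dose permission for Grade 3. The opposite reading is also available: 6.2.1 limited to its cited definition, with the specific hepatic rule controlling. That reading gives the less cautious result.

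The second reply is that safeguards would catch the case. A suspected DLT must reach the Study Chair within 24 hours (5.5). Liver tests are done before each pevonedistat dose, and at least every other day after a Grade 2 to 4 elevation (8.1). The study chair's DLT evaluations are reviewed on a weekly call (14.3.2). Both candidate rules require recovery first. These points stand and lower the risk. They make it likely that someone central knows of the event, but they do not supply the rule that person should apply.

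The third reply is that the sponsor may want to keep the same dose, since 6.2.4 anticipates transient rises after the first infusion. That is a legitimate clinical choice, but it should be stated, and it sits awkwardly with calling the event dose-limiting.

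**Conclusion.** The text is wrong as written, and the fault is minor. For a patient under 12 months with an attributable Grade 3 liver elevation on or after Cycle 1 Day 8 that recovers within the cycle, the protocol permits full-dose re-treatment after a DLT, although reduction appears to be intended. The difference is one dose level: 25% higher at level 3, 40% higher at level 4. These are dose differences, not estimates of harm.

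The reach is small. The ceiling is 12 evaluable infants, none had enrolled by 6/30/19, the patient must still be under 12 months when the DLT occurs, and Part A2 closes once two evaluable patients at a lagging level have a DLT. The expected count of about one rests on borrowing the rate in older children.

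Two stronger inferences should be resisted. One is that the dose-finding is compromised: whether the event is a DLT is settled by 5.6.2.1, so DLT counting, Part A2 closure and the MTD do not depend on which dose follows. The other is that 6.2.5 shares the fault, because it lets treatment resume at Grade 2 hypophosphatemia, a grade that can itself be a DLT in infants. Section 6.2.5 is only a minimum condition after Grade 3 or worse, and for a DLT the recovery requirements in 6.2.1 and 6.2.3, including return to baseline, already largely cover the case.

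**What to change.** Two wording changes:

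1. In 6.2.1, refer to Section 5.6.1 or 5.6.2, so that the reduction rule reaches DLTs defined only for infants.
2. In 6.3, add: *For a Grade 3 ALT/AST/bilirubin DLT in a patient under 12 months, Section 6.2.1 (next lower dose level, with its recovery criteria) applies and the same-dose provision of 6.2.4 does not.*

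Leave 6.2.4 as it is for patients 12 months or older and for recovering Grade 2 elevations in infants. Do not add a separate resume limit of Grade 1 or less. For bilirubin that would be looser than 6.2.1, which asks for eligibility values or baseline: eligibility (4.1.7.3) allows no more than the ULN, whereas Grade 1 in Appendix III runs to 1.5 times ULN. No change to 6.2.5 is needed.

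The change needs no extra patients, visits or samples. Its cost is that a few infants will receive a lower dose than 6.2.4 would have allowed. If the sponsor prefers the same dose for this event, one sentence in 6.3 saying so would also remove the ambiguity, but it would accept full-dose re-treatment after an infant liver DLT.

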7.0 SUPPORTIVE CARE AND OTHER CONCOMITANT THERAPY**7.1 Concurrent Anticancer Therapy**

Concurrent cancer therapy, including chemotherapy, radiation therapy, immunotherapy, or biologic therapy may NOT be administered to patients receiving study drug. If these treatments are administered the patient will be removed from protocol therapy.

7.2 Investigational Agents

No other investigational agents may be given while the patient is on study.

7.3 Supportive Care

Appropriate antibiotics, blood products, antiemetics, fluids, electrolytes and general supportive care are to be used as necessary. See [Section 4.2.7](#) for drugs that should not be used concomitantly due to potential interactions with pevonedistat and irinotecan. See [Section 5.1](#) and [Appendix VIII](#) for diarrhea prophylaxis and treatment recommendations.

7.4 Growth Factors

Growth factors that support platelet or white cell number or function can only be administered in accordance with [Section 6.1.1](#) or for culture proven bacteremia or invasive fungal infection. The Study Chair should be notified before growth factors are initiated.

7.5 Concomitant Medications

Strong CYP3A4 inducers (see [Appendix VII](#)) are prohibited for the duration of the study. Strong inducers of CYP3A4 should be discontinued within 14 days prior to the first dose of pevonedistat.

Concomitant use of strong inhibitors of CYP3A4 (see [Appendix VII](#)), UGT1A1 inhibitors (such as diclofenac, ketoconazole, probenecid, silibinin, tacolimus, nilotinib, and atazanavir), and BCRP inhibitors (cyclosporine, eltrombopag, gefitinib) also should be avoided because of potential for increased irinotecan toxicity.

Acetaminophen may be used judiciously but should not exceed a dose of 37 mg/kg/day (maximum 2 g in 24 hours).

8.0 EVALUATIONS/MATERIAL AND DATA TO BE ACCESSIONED

8.1 Required Clinical, Laboratory and Disease Evaluation

All clinical and laboratory studies to determine eligibility must be performed within 7 days prior to enrollment unless otherwise indicated. Laboratory values used to assess eligibility (see [Section 4.0](#)) must be no older than seven (7) days at the start of therapy. Laboratory tests need **not** be repeated if therapy starts **within** seven (7) days of obtaining labs to assess eligibility. If a post-enrollment lab value is outside the limits of eligibility, or laboratory values are older than 7 days, then the following laboratory evaluations must be re-checked within 48 hours prior to initiating therapy: CBC with differential, bilirubin, ALT (SGPT) and serum creatinine. If the recheck is outside the limits of eligibility, the patient may not receive protocol therapy and will be considered off protocol therapy. Imaging studies must be obtained within fourteen (14) days prior to start of protocol therapy (repeat the tumor imaging if necessary). See [Appendix XIII](#) for Therapy Delivery Maps for Cycle 1 and all subsequent cycles.

Studies to be Obtained	For all patients		For patients \geq 12 months ONLY	For patients $<$ 12 months ONLY
	Pre-Study	During Cycle 1	Prior to Subsequent Cycles [^]	Prior to Subsequent Cycles [^]
History	X	X	X	X
Physical exam with vital signs ⁷	X	Weekly	X	X
Height, weight, BSA	X		X	X
Performance status	X		X	X
CBC, differential, platelets	X	Twice weekly ¹	Weekly ^{1,2,3}	Weekly ^{1,2,3}
Electrolytes including Ca ⁺⁺ , PO ₄ , Mg ⁺⁺	X	Weekly	X	Weekly
Creatinine	X	Weekly	X	Weekly
ALT, AST, bilirubin	X	Prior to each dose of pevoneditat, then weekly*	Prior to each dose of pevoneditat, then weekly*	Prior to each dose of pevoneditat, then weekly*
ECHO/EKG	X			
Albumin	X		X	X
Pulse Oximetry	X		X	X
Pregnancy test ⁴	X		X	X
Tumor disease evaluation	X	End of Cycle 1	End of Cycle 2 then every other cycle x 2 then q 3 cycles ⁵	End of Cycle 2 then every other cycle x 2 then q 3 cycles ⁵
Bone Marrow Evaluation ⁸	X	End of Cycle 1	End of Cycle 2 then every other cycle x 2 then q 3 cycles ⁵	End of Cycle 2 then every other cycle x 2 then q 3 cycles ⁵
Pharmacokinetics ⁶ (required)	X	X		
Pharmacodynamics (optional)	X	X		
INR	X			

[^] Studies may be obtained within 72 hours prior to the start of the subsequent cycle.

¹ Twice weekly during Cycle 1. If patients have Grade 4 neutropenia or thrombocytopenia, CBCs should be checked at least every other day until recovery to Grade 3 or until the criteria for dose limiting toxicity are met.

² If patients develop Grade 4 neutropenia, CBCs should be checked every 3 to 4 days until recovery to Grade 3.

³ If patients remain on study for $>$ 4 cycles and \geq Grade 3 cytopenias are not observed, then CBCs may be obtained at the start of subsequent cycles and as clinically indicated.

⁴ Women of childbearing potential require a negative pregnancy test prior to starting treatment; sexually active patients must use an acceptable method of birth control. Abstinence is an acceptable methods of birth control. All women of childbearing potential must have a pregnancy test done every cycle prior to initiation of a new cycle.

⁵ Tumor disease evaluation should be obtained on the next consecutive cycle after initial documentation of either a PR or CR. If the institutional investigator determines that the patient has progressed based on clinical or laboratory evidence, he/she may opt not to confirm this finding radiographically.

⁶ See [Section 8.3](#) for details.

⁷ Vital signs should be checked prior to each pevonedistat infusion. Vital signs will also be assessed at the end of treatment.

⁸ If a solid tumor patient is suspected to have or has a history of bone marrow involvement then a pre-study bone marrow biopsy and/or aspirate is required. This should then be repeated with each tumor disease evaluation if pre-study bone marrow was positive for metastatic disease.

*Check prior to each dose of pevonedistat, then weekly for remaining weeks of cycle. If patients have Grade 2, 3, or 4 ALT/AST/bilirubin on or after Cycle 1 Day 8, AST/ALT/bilirubin should be checked at least every other day until recovery to \leq Grade 1. See [Section 6.2.4](#) for more details.

8.2 Radiology Studies

8.2.1 Central Radiology Review for Response: Patients who respond (CR, PR) to therapy or have long term stable disease (SD) (\geq 6 cycles) on protocol therapy will be centrally reviewed. COG Operations Center will notify the Imaging Center of any patient requiring central review. The Imaging Center will then request that the treating institution forward the requested images for central review. The central image evaluation results will be entered into RAVE for review by the COG Operations Center and for data analysis.

The images are to be forwarded electronically to the Imaging Research Center at Children's Hospital Los Angeles via the ImageInBox.

COG institutions that are not connected via the ImageInBox can send the images on CD ROM or USB flash drive. Submitted imaging studies should be clearly marked with the COG patient ID, study number (ADVL1615), and date and shipped to [name] at the address below:

8.3 Pharmacokinetics (required)

8.3.1 Description of Studies and Assay

Pharmacokinetics (PK) will be performed to determine the PK of pevonedistat in children. Pharmacokinetic analysis will be conducted at a centralized laboratory using a GLP-validated liquid chromatography/tandem mass spectrometry (LC-MS/MS) assay.

Individual pevonedistat plasma concentration-time data will be analyzed using standard noncompartmental methods. The following PK parameters of pevonedistat will be estimated with C_{max} , T_{max} , AUC_{0-24h} , CL/F , half-life, and $AUC_{0-\infty}$ (as data permit). Individual values and descriptive statistics of pevonedistat plasma concentration-time data and PK parameters will be listed and tabulated by treatment/study day. Individual and mean pevonedistat plasma concentration data will also be plotted over time per treatment/study day.

8.3.2 Sampling Schedule (see [Appendix X](#))

Blood samples will be obtained prior to drug administration and at the following time points:

8.3.2.1 All patients

For patients ≥ 10 kg, samples will be obtained at the following time points:

Day 1 of Cycle 1: pre-dose, end of pevonedistat infusion, and at 1, 2, 4, 6-8 and 24 hours post-dose infusion.

Day 8 of Cycle 1: pre-dose, end of pevonedistat infusion, and at 1, 2, 4, 6-8 and 24 hours post-dose infusion.

Day 10 of Cycle 1: pre-dose

For patients < 10 kg, samples will be obtained at the following time points:

Day 1 of Cycle 1: pre-dose; end of infusion; and at 2, 6-8, and 24 hours post-dose infusion.

Day 8 of Cycle 1: pre-dose; end of infusion; and at 2, 6-8, and 24 hours post-dose infusion.

Day 10 of Cycle 1: pre-dose

8.3.3 Sample Collection and Handling Instructions

Blood samples (3 mL) will be collected into a chilled Becton-Dickinson Vacutainer K2 EDTA tube at a site distant from the infusion for pharmacokinetic evaluation. Samples cannot be drawn from the 2nd lumen of a multi-lumen catheter through which drug is being administered. Record the exact time that the sample is drawn along with the exact time that the drug infusion begins and ends.

